## Secondary analyses

Secondary multiple regression analysis will be performed with treatment allocation as the main exposure. The following key covariates will be forced into the model: age, APACHE II score, presence of ARDS, vasopressor use at baseline. Additional covariates for inclusion in the model will be selected based on clinical plausibility.

We will undertake a secondary per-protocol analysis. This information will be valuable in differentiation between treatment failure (the treatment did not have the intended effect) and process failure (intervention not delivered as intended).

If there is evidence of a difference in the outcome of cognitive dysfunction between treatment groups, we will use path analysis to attempt to ascertain whether the effect of treatment group assignment on cognitive function is mediated by cerebral oxygenation.

For the exploratory outcomes, we will undertake secondary analyses using multivariate regression analysis with fluid balance as the main exposure and treatment group assignment as a covariate.

At a later stage, we will investigate the relationship between cerebral and tissue oxygenation and cardio-respiratory physiological variables such as heart rate, mean arterial pressure, and arterial oxygen saturation.

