## Study Methods

### Study Design

This will be a randomised, open-label, allocation concealed, pilot trial of conservative fluid administration and deresuscitation compared with usual care in adult patients who are critically ill. The intervention will consist of 2 stages: (1) conservative fluid administration and, if appropriate criteria are fulfilled, (2) deresuscitation in the form of diuretics or fluid removal using RRT to target a negative fluid balance.

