### Randomisation

Patients will be randomised a minimum of 24 hours and a maximum of 48 hours following ICU admission. Randomisation will be stratified by study site. Subjects will be randomised in a 1:1 ratio using blocks of variable size.

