### Sample Size Calculation

Based on data from a recent observational study in a similar population [2], we anticipate a fluid balance in the 24 hours up to day 3 (primary outcome) of  $494 \pm 1512$  mL in the usual care group. A sample size of 174 subjects (87 in each group) will have 90% power at a two-tailed significance level of 0.05 to detect a difference in fluid balance of 750 mL over 24 hours. We have allowed for a drop-out rate of 3% and the study will therefore require a total of 180 patients (90 in each group).

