## Outcome measures and analysis

The primary endpoint is the fluid balance (mL) during the 24-hour period up to the beginning of study day 3 [continuous variable, measured using a Student's t-test for independent samples].

Secondary Outcomes		
Feasibility outcomes		
Cumulative fluid balance (mL) from ICU admission until the beginning of study days 3 and day 5, and at ICU discharge	Continuous variables	Independent samples t-test (or non-parametric equivalent)
Rates of recruitment as a proportion of patients screened and as a proportion of all patients admitted to ICU (per site)		Descriptive only
Incidence of significant protocol violations (total number of patients, per site, and by nature of protocol violation)		Descriptive only
Safety outcomes		
Incidence of serious adverse events (SAEs) (number of patients with SAEs as a proportion of total)		Chi-squared test / Fisher's exact test
Incidence of adverse events (AEs) (number of patients with AEs as a proportion of total)		Chi-squared test / Fisher's exact test
Efficacy outcomes		
Change in SOFA scores from baseline to the beginning of day 3 and beginning of day 5, overall and individual organ sub scores	Continuous variable	Multiple regression analysis (with baseline scores as covariate)
Mortality (28-day and 180 day)	Discrete variable	Chi-squared test; Kaplan-Meier survival curves; log-rank test +/- Cox proportional hazards model if assumptions met
Duration of mechanical ventilation in survivors and non-survivors	Continuous variable	Independent samples t-test (or non-parametric equivalent); Kaplan-Meier survival curves; log-rank test; +/- Cox proportional hazards model if assumptions met
Length of ICU stay	Continuous variable	Independent samples t-test (or non-parametric equivalent); Kaplan-Meier survival curves; log-rank test; +/- Cox

		proportional hazards model if assumptions met
Incidence of new acute kidney injury defined as KDIGO Stage 3 (before and after correction for fluid balance) up to the beginning of day 5	Discrete variable	Chi-squared test
Cognitive dysfunction at 180 days	Discrete variable	Chi-squared test
Health-related quality of life (HR-QoL) at 180 days	Ordinal variable	Mann-Whitney test
Incidence of anxiety and depression	Discrete variable	Chi-squared test
Incidence of Post-traumatic stress disorder	Discrete variable	Chi-squared test
Exploratory outcomes		

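### The secondary adjusted model is left open: extra covariates are neither listed, timed nor limited to baseline, and the forced set omits study site and the baseline value of the outcome

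*SAP*

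**What the plan says.** The Secondary analyses section of the SAP sets out a multiple regression with treatment allocation as the main exposure. Four covariates are always included: age, APACHE II score, ARDS and vasopressor use. Only the last of these carries an explicit reference to baseline. The section then continues: "Additional covariates for inclusion in the model will be selected based on clinical plausibility". It does not say which or how many further covariates may enter, when they are chosen, whether the person choosing has seen outcomes by arm, or whether they must predate randomisation. It also does not name the outcomes to which the regression applies.

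Four other places bear on the point:

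- Study Design: "This will be a randomised, open-label, allocation concealed, pilot trial". It describes the second stage of the intervention as "deresuscitation in the form of diuretics or fluid removal using RRT to target a negative fluid balance".
- Randomisation: allocation is stratified by study site. Site is not among the forced covariates.
- Outcome measures and analysis: the primary endpoint is "measured using a Student's t-test for independent samples", so it has no covariates. Baseline adjustment is specified there for change in SOFA only.
- Table 1 of the dummy tables lists characteristics at randomisation, including baseline SOFA and cumulative fluid balance. Nothing ties that list to the regression.

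**The concern.** In a randomised comparison, covariate adjustment is there to gain precision and to reflect the stratification. It does this with a valid error rate if the covariates are fixed without regard to the results and are measured before treatment can affect them. The SAP secures neither condition.

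Clinical plausibility excludes little in critical illness. Most of Table 1 would qualify (SOFA, lactate, KDIGO stage, oxygenation index, sepsis, admission type), and so would several variables that arise only after randomisation. Later diuretic or RRT use predicts fluid balance, but it is also how the intervention works, so conditioning on it would remove part of the effect being estimated. Because the trial is open-label, blinding does not protect a late choice of model, and the SAP puts no other safeguard in its place.

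Meanwhile the two adjustments with the clearest case in this design, study site and the baseline value of the outcome, are left to discretion.

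At stake is whether the adjusted estimate can serve as a check on the primary result. If a reader cannot tell whether the model was fixed or picked, it cannot.

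**Working it through.** **1. The plan's own figure.** The SAP claims "90% power at a two-tailed significance level of 0.05 to detect a difference in fluid balance of 750 mL over 24 hours", with SD 1512 mL and 87 per group.

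- Normal approximation: n per arm = 2 × (1.960 + 1.282)² × 1512² / 750² ≈ 85.4, rounded up to 86. The t-based solution is 86.4, rounded up to 87, or 174 in total, as stated.
- Power at 87 per arm is 90.5% (normal) or 90.2% (t).
- Drop-out: 174 / 0.97 = 179.4, rounded up to 180, as stated.

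The sample size reproduces. It rests on the unadjusted t-test, so the covariate rule does not affect it.

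**2. How far could selection move the error rate?** The SAP gives neither the number nor the strength of the optional covariates, so both are assumed. The simulation has 174 patients allocated 1:1 and no treatment effect. There are four forced covariates and k optional baseline covariates, all independent and equally prognostic, with total explained variance R². The outcome is y = Σ b·x + √(1 − R²)·e, with b = √(R² / (k + 4)). All 2^k subsets of the optional covariates are fitted and the smallest two-sided p for treatment is kept. There were 4,000 trials per setting for k = 3 and 2,000 for k = 5.

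| k (models) | R² | Optional share, R²·k/(k+4) | Four forced only | Best of all subsets |
|---|---|---|---|---|
| 3 (8) | 20% | 8.6% | 5.0% | 8.0% |
| 3 (8) | 40% | 17.1% | 5.3% | 10.2% |
| 3 (8) | 60% | 25.7% | 4.9% | 11.7% |
| 5 (32) | 20% | 11.1% | 5.5% | 10.0% |
| 5 (32) | 40% | 22.2% | 5.2% | 13.9% |
| 5 (32) | 60% | 33.3% | 5.7% | 17.5% |

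Simulation error is small against these differences: √(0.08 × 0.92 / 4,000) = 0.4 points for the first row and √(0.175 × 0.825 / 2,000) = 0.8 points for the last.

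Two further results set the limits:

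- Entering all optional covariates as one fixed set also gave 4.9–5.7%. The inflation comes from choosing among models on their results, not from having more covariates.
- The table counts results in either direction. In a separate run with four or six optional covariates, counting only results that favour one arm gave 4.2–7.6% against a nominal 2.5%.

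**3. What would a post-randomisation covariate do?** Suppose it carried a share m of the 750 mL effect, with the SD held at 1512. The standard error of the difference is 1512 × √(2/87) ≈ 229 mL, and power = Φ(difference / 229 − 1.96).

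| m | Remaining difference | Power at 87 per arm |
|---|---|---|
| 0 | 750 mL | 91% |
| 25% | 563 mL | 69% |
| 50% | 375 mL | 37% |
| 75% | 188 mL | 13% |

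The shares are illustrations. The SAP gives no basis for any of them.

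**The case against.** The strongest reply is that clinical plausibility is a subject-matter criterion, not selection on p-values. Applied once, without looking at results, it yields a fixed set, and the simulation shows that a fixed set keeps its error rate. This stands. The higher figures describe the worst use of the rule, not the rule itself.

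Two stronger readings are tempting, and the SAP does not support them:

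- A reader might infer that covariates will be chosen once results are known. The SAP gives no time of selection. It permits a late choice but does not plan one.
- A reader might infer that the sponsor intends to adjust for the intervention's own mechanism, because the same section has a regression with fluid balance as exposure and treatment group as covariate. That is a separate analysis confined to the exploratory outcomes. The path analysis of cognitive function is likewise its own declared mediation question. No sentence proposes diuretics, RRT or later vasopressor use as covariates here, and the four named covariates are of a kind recorded at or before randomisation.

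A concern about too few deaths per model term would also go too far. The SAP states no expected mortality and does not say that this regression covers mortality.

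It can also be said that adding site and a baseline value is a matter of preference. In part it is, but site is the trial's own stratification factor and the SAP already adjusts SOFA change for baseline, so both follow from choices made elsewhere in the same document.

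**Conclusion.** The point holds as a weakness in how a secondary analysis is specified. The SAP does address covariate choice, but with a discretionary rule that has no list, time point or baseline limit, in an open-label trial. The forced set omits study site and the baseline value of the outcome.

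If the rule were used to report the most favourable model, the false-positive rate would be 8% in the mildest setting and roughly 10–17% in the others. This assumes three to five independent optional covariates and 20–60% explained variance, and it is an upper bound. With a set fixed in advance the rate stays near 5%. Loss of effect through a post-randomisation covariate is possible under the wording but is not planned.

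This is a trial that its SAP calls a pilot, and the primary comparison and its sample size do not depend on this model. The importance is therefore moderate, and the main reason to act is that the remedy costs almost nothing.

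**What to change.** Replace the open sentence in Secondary analyses, before database lock, with a closed specification:

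- The adjusted model contains treatment, age, APACHE II, ARDS at randomisation, vasopressor use at baseline, study site, and the baseline value of the outcome where one exists. State what counts as that value for the 24-hour fluid balance, since Table 1 lists a cumulative baseline balance and not a 24-hour one.
- Only variables measured before randomisation may enter.
- Any other adjusted model is reported as post hoc and labelled so.

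The cost is a short SAP edit and the loss of freedom to add covariates later without a label. Site uses one degree of freedom fewer than the number of sites, which the SAP does not give. For a continuous outcome with 174 patients, the intercept, treatment, four covariates and a baseline value leave 174 − 7 = 167 before site is taken off. The primary analysis and the sample size need no change.

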## Objectives

1. To determine the feasibility, safety and clinical outcomes of conservative fluid administration and deresuscitation compared with usual care in critically ill patients
2. To explore biological effects of conservative fluid administration and deresuscitation.

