Plasma levels of markers of endothelial injury (Angiopoietin I/II and Ang-1/2, Syndecan-1, total protein, plasma albumin, and protein permeability (albumin: $\alpha$ 2-macroglobulin ratio)), absolute levels and change from baseline	Continuous variables	Independent samples t-test (or non-parametric equivalent); Repeated measures ANOVA if applicable. Scatterplots and Pearson's correlation coefficient or non-parametric alternative if applicable.
Plasma levels of Inflammatory mediators e.g. CRP, TNF $\alpha$ , IL6, IL8: absolute levels and change from baseline	Continuous variables	Independent samples t-test (or non-parametric equivalent); Repeated measures ANOVA if applicable. Scatterplots and Pearson's correlation coefficient or non-parametric alternative if applicable.
Cardiac function (echocardiographic measures including left ventricular ejection fraction, E/E' ratio)	Continuous variables	Independent samples t-test (or non-parametric equivalent)
Renal function and injury (plasma and urine levels of Cystatin C and NGAL), absolute levels and change from baseline	Continuous variables	Independent samples t-test (or non-parametric equivalent); Repeated measures ANOVA if applicable. Scatterplots and Pearson's correlation coefficient or non-parametric alternative if applicable.
Cerebral oximetry (NIRS measurement of regional cerebral oxygen saturation), mean and minimum rScO 2 level, proportion of time spent with rScO 2 below thresholds of 50%, 65%, and 75%	Continuous variables	Independent samples t-test (or non-parametric equivalent)
Tissue oxygenation (NIRS measurement of muscle tissue oxygen saturation), mean and minimum rScO 2 level	Continuous variables	Independent samples t-test (or non-parametric equivalent)

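### The secondary regressions of exploratory outcomes on fluid balance name no severity covariate and no fluid-balance window, so the slope is an observational association open to confounding by severity of illness.

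*SAP*

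**What the plan says.** Two regression models appear under Secondary analyses in the SAP, and they are specified differently.

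- **Allocation model.** "Secondary multiple regression analysis will be performed with treatment allocation as the main exposure". It has a fixed severity set: "The following key covariates will be forced into the model: age, APACHE II score, presence of ARDS, vasopressor use at baseline". It also has an open-ended one: "Additional covariates for inclusion in the model will be selected based on clinical plausibility".
- **Fluid-balance model.** This is an additional, secondary model applied to the exploratory endpoints, and the plan describes it as "multivariate regression analysis with fluid balance as the main exposure and treatment group assignment as a covariate". No other covariate is named, nothing says that the four forced covariates carry over, and the period over which fluid balance is measured is not given.

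The exploratory part of the table under Outcome measures and analysis separately lists a between-arm test for every exploratory outcome. For the endothelial, inflammatory and renal markers the entry begins "Independent samples t-test (or non-parametric equivalent); Repeated measures ANOVA if applicable", and these markers are to be analysed both as absolute levels and as change from baseline. For echocardiography and for cerebral and tissue oximetry only the two-sample test is listed, with no mention of a baseline value.

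These outcomes serve the second objective: "To explore biological effects of conservative fluid administration and deresuscitation".

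**The concern.** The model whose exposure is randomised is given severity covariates. The model whose exposure is not randomised, and which needs them more, is given none. Sicker patients may plausibly retain more fluid and also have worse endothelial, inflammatory, renal and oxygenation measures. A slope adjusted for treatment group alone would then differ from zero even if fluid balance had no effect on any marker.

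The SAP sets one significance threshold of 0.05 (Statistical analysis principles) and does not say that this slope is to be read as an association. A reader of the later manuscript could take a significant slope as evidence of a biological effect of fluid. The model covers a whole family of markers, so the same bias could recur across many results.

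**Working it through.** **1. The plan's own figure.** Inputs from Sample Size Calculation: difference 750 mL, SD 1512 mL, two-sided 0.05, power 90%. Per arm, n = 2 × (1.960 + 1.282)² × 1512² / 750² = 85.4, so 86. With the t distribution it is 86.4, so 87 per arm and 174 in all. Allowing 3% drop-out, 174 / 0.97 = 179.4, so 180. The stated sample size is reproduced and is not in question.

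**2. Where the slope's information comes from.** At 1:1 allocation with a common SD, the share of fluid-balance variance due to arm is (750/2)² / [(750/2)² + 1512²] = 140,625 / 2,426,769 = 5.8%. The other 94.2% lies within arms. Once arm is in the model, only this within-arm part informs the fluid-balance slope, and none of it is randomised. The figure applies to the primary endpoint's 24-hour window and assumes that the planned difference occurs.

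**3. What confounding could do.** Let severity correlate r_f with fluid balance within arm and r_m with the marker, and let neither fluid balance nor arm affect the marker. In SD units the slope given arm is then expected to be r_f × r_m instead of zero. Both correlations are assumptions; the SAP gives neither. In 4000 simulated trials per row, each with 174 patients who all have the marker, the proportions with p < 0.05 were:

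| r_f, r_m (assumed) | Expected slope | Fluid balance, adjusted for arm | Fluid balance, adjusted for arm and severity | Between-arm test |
|---|---|---|---|---|
| 0, 0.3 | 0 | 5.2% | 5.6% | 4.5% |
| 0.1, 0.3 | 0.03 | 7.5% | 5.3% | 5.4% |
| 0.2, 0.3 | 0.06 | 11.7% | 4.7% | 5.2% |
| 0.3, 0.3 | 0.09 | 21.9% | 4.2% | 4.6% |
| 0.4, 0.4 | 0.16 | 54.8% | 4.9% | 5.6% |
| 0.5, 0.5 | 0.25 | 91.4% | 4.8% | 4.6% |

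A hand check of the 0.3, 0.3 row: with 171 residual degrees of freedom the test statistic centres on 0.09 × √(171 / (1 − 0.09²)) = 1.18, and 1 − Φ(1.96 − 1.18) is about 22%.

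**4. What adjustment can achieve.** The return to 5% in the fourth column assumes that severity is one perfectly measured variable. With a proxy that correlates k with severity, the expected slope is r_f × r_m × (1 − k²) / (1 − r_f² × k²). It shrinks as k rises but reaches zero only at k = 1. Age, APACHE II, ARDS and vasopressor use are proxies, so they would reduce the bias without removing it.

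**5. The window.** The SAP defines several fluid balances: the 24 hours up to the beginning of day 3, and cumulative totals from ICU admission to day 3, to day 5 and to ICU discharge. Randomisation takes place 24 to 48 hours after admission, so each cumulative total includes at least 24 hours that allocation could not influence. Every window leaves the exposure non-randomised, but the slope means something different in each.

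**6. Baseline adjustment of the between-arm tests.** Let r be the correlation between baseline and follow-up marker, with equal variances. Relative to comparing absolute levels (1), the variance of the arm contrast is 2(1 − r) for change scores and 1 − r² for ANCOVA. Since 1 − r² = (1 − r)(1 + r) ≤ 2(1 − r), ANCOVA is no less precise than either listed version, apart from the small cost of estimating one more coefficient. The SAP already takes this approach for change in SOFA score.

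**The case against.** The strongest reply is that this is a secondary model of exploratory outcomes in a pilot trial, additional to between-arm tests that answer the second objective by randomised comparison. That stands, and it limits the importance of the point. A reader might infer that the plan gives up the randomised contrast for these markers. It does not: the contrast is absent only from the fluid-balance slope, and the table keeps a two-sample test for every exploratory outcome.

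It can also be said that naming one covariate does not exclude others, and that change from baseline already uses the baseline marker. Both are partly right. However, open covariates leave the choice until after the data are seen, and a change score is not the same as adjusting for baseline. Nor can the exposure be called purely post-randomisation, because no window is given and some candidate windows begin at ICU admission.

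Treatment group as a covariate is defensible. Under Study Design the strategy includes diuretics and fluid removal by renal replacement therapy, which could act on markers by routes other than net balance. For the same reason, a reader tempted to use allocation as an instrument for fluid balance should hesitate: that method needs allocation to act through fluid balance alone. It would also be imprecise. The expected first-stage t is (750/1512) × √(87/2) = 3.3, so F is about 11, and standard errors would be roughly 1/√0.058, or about 4 times, larger.

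**Conclusion.** The point holds for this one model. As written, its fluid-balance slope is a within-arm observational association, the only named covariate is treatment group, and suitable severity covariates appear in the same section for a different model.

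The 5.8% and 94.2% split follows from the SAP's own figures, given a common SD and the planned difference. The false-positive rates of 7.5% to 91% do not: they depend on assumed correlations, and they show the direction of the risk, not its size in this trial. A reader might infer that severity is certain to distort these results, but the SAP holds no data that would show it. The primary endpoint, sample size, safety outcomes and clinical outcomes are untouched.

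**What to change.** Amend the fluid-balance paragraph under Secondary analyses to:

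- state the window over which fluid balance is measured for this model;
- include "age, APACHE II score, presence of ARDS, vasopressor use at baseline" as covariates, and keep treatment group;
- add the baseline marker value for the endothelial, inflammatory and renal markers, where the outcome table shows that it is collected. The table does not show this for echocardiography or oximetry, so it should not be assumed there;
- say that the slope will be reported as an observational association, beside the between-arm comparison and with residual confounding acknowledged.

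In the exploratory part of the outcome table, adjust the between-arm comparisons of the endothelial, inflammatory and renal markers for baseline (ANCOVA).

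The cost is SAP wording and a few more model terms. The four covariates are already needed for the allocation model, and the baseline markers for the change scores. Neither the sample size nor the primary analysis changes.
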